5. OBJECTIVE(S)

PRIMARY

To compare PICO against tNPWT for the percentage change in the target ulcer area over the 12-week treatment period from baseline

KEY SECONDARY

CONFIDENTIAL DOCUMENT
This document contains confidential information, which is the property of Smith & Nephew, Inc. Do not copy, disclose, or circulate without written authorization from the appropriate Smith & Nephew personnel

To compare PICO against tNPWT for the percentage change in the target ulcer depth and volume over the 12-week treatment period from baseline

SECONDARY

1. To compare PICO against tNPWT in the time (days) to achieve confirmed complete target ulcer closure by either surgical intervention or secondary intention
2. To compare PICO against tNPWT for the proportion of subjects that achieve confirmed complete target ulcer closure by either surgical intervention or secondary intention
3. To compare PICO against tNPWT for differences in Health Related Quality of Life (HRQoL) over the 12-week treatment period

EXPLORATORY: Assessment of a difference in the following target ulcer assessments weekly over 12-week treatment period and to compare PICO against tNPWT:

- Condition of the target ulcer peri-wound skin
- Estimation of tissue types present on the target ulcer
- Clinical signs and symptoms of infection on the target ulcer
- Incidence of target ulcer infection
- Pain on removal of the dressing
- Pain on initiation of therapy/during dressing wear
- Dressing wear time
- Additional interventions
- Impact of the device on aspects of daily living and satisfaction with device therapy

SAFETY: Adverse events associated with the target ulcer area and all AE judged to be serious (SAE) will be recorded

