9.1 VISITS AND EXAMINATIONS

9.1.1 Screening Run-in Visit 1

Assign a subject ID number to each subject who enters screening.

NOTE 1: Subjects who enter screening should have the potential heal, with excessive edema and infection under control.

NOTE 2: Any subject who signs an informed consent, but fails to meet the required entry criteria is considered to be a Screen Failure. Screen Failure subjects should have their demographic information captured with the reason for screen failure specified. Subjects may be re-screened 2 times. If a subject fails to meet all criteria after 3 screening attempts, the subject may not be enrolled into the study. A new informed consent is required for each screening attempt. All procedures, excluding the central lab, ABI, Toe Pressure, or TcPO₂ obtained within 30 days of re-screening, must be repeated for each screening attempt.

1. Explain the purpose and nature of the study, and have the subject or the subject's legally authorized representative **read, sign, and date** the IRB-approved informed consent document. Additionally, have the individual who obtains consent from the subject sign and date the informed consent document. Provide a photocopy of the signed informed consent document to the subject and place the original signed document in the subject's chart. Documentation of the informed consent process should be captured in each subject's source for each consenting.

----- Do not proceed until consent has been obtained -----

2. Screen the subject against the protocol inclusion and exclusion criteria for eligibility.
3. Obtain basic demographic information and relevant medical history, including information on all concomitant medications.
4. Complete a physical examination, body weight, height, and vital signs, including measurement of resting heart rate, respiratory rate, and blood pressure while seated.
5. Obtain complete history pertinent to the lower extremity target ulcer, including duration of the target ulcer, previous and current treatment and any other history that may have impacted the target ulcer (has it healed and re-occurred in the same location).
6. Assess target ulcer level of pain using the VAS.
7. Perform ulcer debridement if indicated. Debridement may only be performed using a curette, scissors, scalpel, or forceps.

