9.1.2 Screening Run-in Visit 2 [± 1] Days After Screening Run-in Visit 1]

At Screening Run-in Visit 2 the following procedures will be performed prior to randomization, to assure that none of the exclusion criteria described in Section 7.3.1 are met. The Screening Run-in Visit 2 should occur at 7 (± 1) days after Screening Run-in Visit 1. The day on which this visit occurs will set the weekly visit day for all subsequent treatment Visits 2 through 12 if the subject is randomized. A (± 1) day visit window will be allowed. Subjects who do not return on the original day of the week for a scheduled visit at Study Visits 2-12 should be brought back on the original scheduled day at the subsequent visit. Subjects who do not meet all eligibility criteria will be considered screen failures and documented as such. Subjects who meet all entry criteria will complete the randomization procedure and this visit will then serve as Study Visit 1.

1. Subjects will be queried regarding any changes in general health and the use of concomitant medications.
2. If any adverse events in the target wound have occurred as a result of the screening or run-in procedures, since the last assessment, the events must be reported and evaluated as instructed in Section 12, *Adverse Events*.
3. Remove compression bandaging (**for VLU subjects**) and topical dressing (**both VLU/DFU subjects**) to assess the target ulcer.

Examine the ulcer for evidence of infection. If signs/symptoms indicate infection, remove the subject from the Run-in period as a screen failure.
4. Assess level of pain, post dressing removal, using the VAS.
5. Debride the ulcer if indicated, at the discretion of the Investigator.

After debridement if presence of necrotic tissue or eschar within the target ulcer, subject should be screen failed.
6. Photograph and determine the post-debridement ulcer area (cm²), perimeter (cm), greatest depth (mm), volume (cm³) and maximum linear dimension (cm) using the ARANZ Silhouette wound imaging and measurement device. This is the baseline

CONFIDENTIAL DOCUMENT
This document contains confidential information, which is the property of Smith & Nephew, Inc. Do not copy, disclose, or circulate without written authorization from the appropriate Smith & Nephew personnel

ulcer assessment measurement.

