All responses to the exit survey will be summarized by treatment and by individual tNPWT device. In addition, where appropriate, a Cochran-Mantel-Haenszel test will be used to test for a difference in subject response between treatments for individual survey questions.

Remaining exploratory endpoints, including the estimation of tissue types present, condition of peri-wound skin and the pain on removal of dressing and at initiation of, and during, therapy, will be summarized by assessment and treatment.

CONFIDENTIAL DOCUMENT
This document contains confidential information, which is the property of Smith & Nephew, Inc. Do not copy, disclose, or circulate without written authorization from the appropriate Smith & Nephew personnel

Other Planned Analysis

At minimum, all data collected will be summarized and listed by treatment; where appropriate data collected will also be summarized by tNPWT device. Additional subsets for summaries may be utilized as a result of the analyses relating to the primary and secondary objectives.

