4.2 Statistical Methods

Unless otherwise specified, all analyses will be performed in SAS v9.4 (or later).

Where data summaries are specified, categorical and ordinal variables will be summarized using frequency distributions which will detail the number and percentage of subjects which fall into each category. Continuous variables will be summarized using the following summary statistics: mean, median, standard deviation, minimum and maximum values, and number of observations.

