The standardised residuals will be assessed for normality (histograms, quantile-quantile plots), homoscedacity (plots against regressors) and no large outliers (magnitude, covariance ratio, DFBETAS). Should these assumptions not hold or if N<20 then non-parametric bootstrapping may be applied to generate 95% confidence intervals of the model estimates. If these differ widely from those of the linear regression model then the bootstrapping estimates will be used these will be used.

The average wear time per subject (at a subject level) will be summarized by treatment, wound type, and the remaining covariates detailed in the previous paragraph. The duration of dressing wear (at a dressing level) will also be summarized by treatment, center, wound type, level of mobility at baseline, level of exudate at the previous assessment and ulcer area (categorized) at the previous assessment.

ST:

9 7 5

Reference:

CE/052/PIC

Customer Code:

0 5

Impact of the device on aspects of daily living and satisfaction with device therapy

All response questions to the exit survey will be summarized by treatment, center, wound type and baseline level of mobility.

A Cochran-Mantel-Haenszel will be used to test for a difference between treatments in individual responses to the Exit Survey for: Overall satisfaction, Opinion of using the device on another wound in future, comfortable to wear, activity level change, and the use of the NPWT device was disruptive to my sleep.

Pain on removal of dressing, at initiation of therapy and during wear

The level of pain on initiation of therapy will be summarized by Study Visit and treatment, separately for each wound type and overall.

The level of pain on initiation of therapy will also be summarized for the ActiV.A.C.® treatment arm overall Study Visits by whether intermittent or continuous therapy is applied, and by pressure range applied (for intermittent – the high therapy pressure value will be used), and compression rate, at the current Study Visit.

The level of pain during wear, and on removal, will be summarized by Study Visit and treatment, separately for each wound type and overall.

The level of pain during wear, and on removal, will also be summarized for the ActiV.A.C.® treatment arm overall Study Visits by whether intermittent or continuous therapy is applied, and by pressure range applied (for intermittent – the high therapy pressure value will be used), and compression rate, at the current Study Visit.

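### Dressing pain is a stated PICO versus tNPWT comparison, but the plan only summarizes it by visit and arm, with no pre-specified difference, confidence interval or baseline adjustment

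*Protocol*

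**What the plan says.** **Objective.** Protocol section 5 introduces its exploratory list as "Assessment of a difference in the following target ulcer assessments weekly over 12-week treatment period and to compare PICO against tNPWT". The list includes pain on dressing removal and "Pain on initiation of therapy/during dressing wear". SAP 1.1 carries the same list, with ActiV.A.C. named as the comparator. The endpoint definitions in Protocol 9.4 and SAP 2.3.3 again describe a comparison between treatments and name all three pain measures.

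**Data collected.** Wear, removal and initiation pain are scored on a VAS at Study Visits 2-12 (Protocol 9.1.4). Initiation pain is also scored at Study Visit 1, after the allocated device is applied (9.1.3). Two scores precede allocation: at Run-in Visit 1, "Assess target ulcer level of pain using the VAS", and at Run-in Visit 2, "Assess level of pain, post dressing removal, using the VAS".

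**Analysis.** Protocol 10.3.3 says that "the pain on removal of dressing and at initiation of, and during, therapy, will be summarized by assessment and treatment". SAP 4.11 says "The level of pain on initiation of therapy will be summarized by Study Visit and treatment, separately for each wound type and overall" and "The level of pain during wear, and on removal, will be summarized by Study Visit and treatment, separately for each wound type and overall". It adds a breakdown within the comparator arm by therapy mode, pressure range and compression rate. SAP 4.2 defines a continuous summary as "mean, median, standard deviation, minimum and maximum values, and number of observations".

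**Pre-randomization pain.** SAP 4.8 compares Run-in Visit 1 pain between groups by t-test or Wilcoxon test. SAP 4.11 summarizes Run-in Visit 2 removal pain by wound type.

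**The concern.** The objective asks how the arms differ in pain. The planned output describes each arm separately and leaves the reader to form the contrast. Other exploratory items get a formal comparison in SAP 4.11: Fisher's exact tests with intervals for infection and for antibiotics or interventions, a regression estimate with a 95% CI for wear time, and Cochran-Mantel-Haenszel tests for selected exit-survey items. In SAP 4.12, total personnel time for application gets a t-test with a 95% CI, although it is not among the listed objectives.

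Pain is an outcome on which two devices with similar healing could still differ for the patient. Without a pre-specified contrast, the report either leaves that comparison unanswered or answers it with a visit or method chosen after the data are seen.

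**Working it through.** **1. Is a between-arm pain estimate planned anywhere?** The summaries in Protocol 10.3.3 and SAP 4.11, read with the definition in SAP 4.2, give location, spread and count per group. The derived-data list in SAP 4.3 touches pain only in item 34, which codes the VAS as 0 where no pain is reported. It defines no change from baseline for pain. Neither document gives a difference, interval, test or model.

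**2. Does pre-randomization pain enter an on-treatment comparison?** Run-in Visit 1 pain is used to check baseline balance. Run-in Visit 2 pain is summarized. Neither is a covariate or the base of a change score. The Run-in Visit 2 score is the natural covariate because it is taken on dressing removal and before allocation.

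**3. Who contributes at each visit?** From Protocol 9.1.4 to 9.1.6 and Table 17-1:
- At Visits 2-12, wear pain (step 3) and removal pain (step 6) are scored before closure is assessed (step 8). An ulcer first found closed at a visit still supplies both scores there. Initiation pain (step 14) is skipped.
- After closure, or a decision to close surgically, the next visit is Visit 14, so the subject supplies no further weekly scores.
- At Visit 13, only subjects whose ulcer is closed or will be surgically closed complete the procedures.
- At Visit 14, wear and removal pain are scored only if the ulcer remained open during treatment.

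The per-visit groups therefore shrink over time. The Visit 13 and Visit 14 rows are split by closure status, which is itself an outcome.

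**4. Is the sample large enough for a useful estimate?** The documents give no sample-size figure for pain. The only one is for the primary endpoint (Protocol section 11): 128 completers, margin 12.5, SD 24.5, 80% power, one-sided 0.025.
- SE = 24.5 × √(2/64) = 4.33, and 12.5/4.33 = 2.886.
- Fixed-design power = Φ(2.886 − 1.960) = 82.3%.
- With an interim at 50% information, efficacy Z 2.963 and futility Z 0.559, power is 80.2%. The stated 80% reproduces.
- 128/(1 − 0.20) = 160 randomized, as stated.

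For pain with 64 per arm: half-width = 1.96 × SD × √(1 − ρ²) × √(2/64), where ρ is the correlation between baseline and outcome. SD and ρ are assumptions.

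| Assumed SD (mm) | ρ = 0 | ρ = 0.5 | ρ = 0.7 |
|---|---|---|---|
| 15 | 5.2 | 4.5 | 3.7 |
| 20 | 6.9 | 6.0 | 4.9 |
| 25 | 8.7 | 7.5 | 6.2 |
| 30 | 10.4 | 9.0 | 7.4 |

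Replacing 1.96 by 1.96 + 0.84 gives the difference detectable with 80% power: 5.3 mm (SD 15, ρ 0.7) to 14.9 mm (SD 30, ρ 0).

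As an illustration of thinning, if half of the 64 per arm still gave a score at a late visit, the half-width would grow by √2 = 1.41. For SD 25 and ρ 0.5 it would go from 7.5 to 10.6 mm.

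**The case against.** The strongest reply is that describing some exploratory endpoints without inference is an ordinary choice, and that pain is not singled out. Tissue types and peri-wound skin fall under the same objective and are also only summarized. This is fair, and it is why the point is minor. It does not remove the mismatch between an objective worded as a comparison and a plan that contains none.

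SAP 2.3.5 also names pain among the ulcer progression parameters and applies LOCF to remaining values that must be analysed at the end of 12 weeks. The plan is therefore not silent on missing pain scores. The rule fills in values at one time point; it does not supply a contrast between arms.

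Four stronger readings are tempting, and the documents do not support them:
- *Baseline pain is ignored.* It is tested at Run-in Visit 1 and summarized at Run-in Visit 2. The general rule in SAP 4.1 that descriptive statistics are given by treatment may extend the Run-in Visit 2 summary to arms. What is missing is its use for adjustment.
- *The trial will yield no pain estimate.* Mean, SD and n per arm and visit allow a crude difference and interval. What is missing is a pre-specified one.
- *Late visits contain only ulcers that failed to close.* The order of steps at Visits 2-12 and the Visit 13 rule contradict this.
- *Some of the many table cells will differ by chance at the 5% level.* No pain test is planned, and the cells overlap across visits and wound-type groupings, so such a count measures nothing in this plan.

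**Conclusion.** The point holds as a gap between objective and analysis. Pain is to be compared between arms, yet no between-arm difference or interval is pre-specified, and no pre-randomization score adjusts on-treatment pain. Per-visit crude differences are a poor substitute because the contributing subjects change with closure.

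The planned sample could support an estimate with a 95% CI half-width of roughly 4 to 10 mm. That range rests on an SD of 15 to 30 mm, a baseline correlation of 0 to 0.7 and 64 subjects per arm. The SD and correlation are assumptions, and fewer scored subjects would widen the interval. The matter is a worthwhile, inexpensive improvement. It is confined to an exploratory objective and has no bearing on the primary conclusion.

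**What to change.** In SAP 4.11, for each of the three pain measures, add one exploratory model in the Full Analysis Set with treatment, randomization stratum and Run-in Visit 2 VAS. Report the PICO minus tNPWT difference with a 95% CI.

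- **Outcome.** Use a repeated-measures model over on-therapy visits with visit as a factor. Alternatively, use each subject's on-therapy mean, with a sensitivity analysis limited to early visits that nearly all subjects attend. The safeguard is needed because the number of visits depends on time to closure.
- **Visits 13 and 14.** State how these scores map to treatment week, since their rows are split by closure status.
- **Study Visit 1.** Treat initiation pain there as an outcome, because it follows application of the allocated device.
- **Distribution.** Use a bootstrap CI if the zero-coded scores make the residuals clearly non-normal.
- **Tables.** Keep the visit summaries as support.

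The cost is three models on data already collected and three more nominal results, labelled exploratory. If the sponsor does not want a comparison, the consistent alternative is to reword the pain objective as descriptive.

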6. TEST ARTICLE

6.1 IDENTIFICATION

Test Article: PICO - Single-Use Negative Pressure Wound Therapy (NPWT) System

Six (6) sizes of dressing are available in kits which contain 2 dressings, 1 pump and secondary fixation strips:

10cm x 20cm / 4in. x 8in. 66800951
10cm x 30cm / 4in. x 12in. 66800952
15cm x 15cm / 6in. x 6in. 66800954
15cm x 20cm / 6in. x 8in. 66800955
15cm x 30cm / 6in. x 11¾in. 66800956
20cm x 20cm / 8in. x 8in. 66800957

PICO Filler Dressings:

PICO foam and gauze filler dressing kits

Control Article: tNPWT devices that have successfully completed a coding verification request with CMS, are portable, FDA cleared, and have the following capabilities (e.g., range of negative pressure, connective tubing, canister, foam or gauze filler, and approved for home use) and have the indication to treat VLU and DFU.

6.2 USAGE

PICO:

The PICO Single Use Negative Pressure Wound Therapy System consists of a pump and two sterile dressing kits. The PICO pump maintains negative pressure wound therapy (NPWT) at -80 mmHg (nominal) +/- 20 mmHg to the wound surface. Exudate is managed by the dressing through a combination of absorption and evaporation of moisture through the outer film.

PICO is intended for use in wound sizes (surface area x depth) up to 400 cm³, which are considered to be low to moderately exuding. The kit is intended to be used for a maximum of 7 days on low exuding wounds and 6 days on moderately exuding wounds. Therapy duration of the kit may be less than indicated if clinical practice or other factors such as wound type, wound

size, rate or volume of exudate, orientation of the dressing or environmental conditions, result in more frequent dressing changes. PICO may be used either with a filler (foam or gauze), placed into the wound where greater granulation stimulation is required, or without any foam or gauze wound filler.

tNPWT:

Please refer to Appendix 18.11 for the list of Sponsor-approved tNPWT devices.

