7.3 EXCLUSION CRITERIA

1. Subjects with known allergies to product components (silicone adhesives and polyurethane films (direct contact with wound), acrylic adhesives (direct contact with skin), polyethylene fabrics and super-absorbent powders (polyacrylates) (within the dressing) or any contraindications with the use of NPWT (see Appendix 18.1).
2. Therapy with another investigational agent within thirty (30) days of Screening (Run-in Visit 1), or during the study.
3. Ulcers which are deemed as highly exuding, per the Investigator's discretion.
4. Current diagnosis of osteomyelitis at the target wound location that is not currently receiving treatment [Documented history of resolved osteomyelitis is allowed].
5. Malignancy in the target ulcer, or history of cancer in the preceding 5 years (other than carcinoma in situ of the cervix or adequately treated non-melanoma skin cancers).
6. Clinical evidence of target ulcer bed infection.
7. Current diagnosis of vasculitis or current diagnosis of claudication.
8. Current systemic therapy with cytotoxic drugs.
9. Current therapy with chronic (> 10 days) oral corticosteroids.
10. Previous treatment with NPWT device or hyperbaric oxygen within 7 days of screening.
11. Per Screening central lab hematology report, WBC < 2.0 x10⁹/L, neutrophils < 1.0 x10⁹/L, platelets < 100 x10⁹/L, and Hgb < 8.0 g/dL.
12. Per Screening central lab chemistry report, serum total bilirubin or serum creatinine ≥ 2 times the upper limit of the normal value (ULN); or, aspartate aminotransferase (AST), alanine aminotransferase (ALT) or alkaline phosphatase ≥ 3 times ULN.
13. The ulcer is in a location that is non-amendable to the creation of an airtight seal for the effective delivery of topical NPWT to the ulcer surface.

14. Subjects with a Venous Leg Ulcer (VLU):

- A. A target ulcer of non-venous etiology (e.g., sickle cell anemia, necrobiosis lipoidica diabetorum, pyoderma gangrenosum, vasculopathic or vasculitic).
- B. Deep Vein Thrombosis (DVT) that is acute, defined as the first 10 days from onset of symptoms, or any DVT for which compression bandaging is considered by the Investigator to be contraindicated.
- C. Refusal of or inability to tolerate compression therapy

15. Subjects with a Diabetic Foot Ulcer (DFU):

- A. Diagnosis of active Charcot foot syndrome
- B. Target wound location on toes

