Record any additional dressings used and rationale for using this dressing.

Type of wound filler dressing if used (foam or gauze-based filler dressing).

Number of personnel used to apply NPWT system.

Time used to apply NPWT system (minutes).

Record level of negative pressure, intensity setting and delivery mode selected for tNPWT subjects, if appropriate for device selected.

Apply Profore compression bandage over the NPWT dressing for VLU subjects only.

5. Record subject's level of pain, during initiation of NPWT therapy, using VAS.
6. Subjects will be instructed to refrain from using excluded medications, and to return to the office for Study Visit 2 in 7 (\pm 1) days.

Subjects using a negative pressure filler dressing will be instructed to complete a dressing change in 2-3 days from application.

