9.1.4 Study Visits 2-12

The treatment period is defined as Randomization Study Visit 1 through Study Visit 12. During the study treatment period, any AE associated with the target ulcer and all SAE of any kind will be recorded in the appropriate eCRF. Device deficiencies (DevD) will be recorded in a separate eCRF. The evaluation of all AE is described in Section 12, *Adverse Events*. All weekly visits

must be performed according to the study visit schedule (Section 17), preferably on the same day each week, to conduct all assessments and to assure compliance with treatment. A plus or minus one day visit window will be used for all study visits.

VLU subjects found to have target ulcer closure should continue the compression dressing. Appropriate treatment for DFU subjects found to have target ulcer closure is left to the Investigator's discretion. Appropriate treatment for VLU and DFU subjects, whose target ulcer is ready for and will be surgically closed, is left to the Investigator's discretion. If the Investigator believes the target ulcer is ready for surgical closure, then this procedure should be completed within the same week of the scheduled study visit. The next scheduled visit for subjects with closed target ulcers or subjects that will be surgically closed will be designated as End of Treatment Assessment Visit 14 and should occur in 7 (± 1) days.

All study procedures should occur in the order outlined in the protocol. Study Visits occurring outside the protocol specified visit window should be completed and recorded as a protocol deviation.

1. Subjects will be queried regarding any changes in general health and the use of concomitant medications.
2. Any AE associated with the target ulcer and all SAE of any kind reported since the last assessment will be recorded in the appropriate eCRF. DevD will be recorded in a separate eCRF (see "Section 12, *Adverse Events*" for reporting and evaluating AE). Also, subjects will be queried as to any additional ulcer-related interventions requiring hospital admission, surgical intervention or specialist referral since the last assessment.
3. Assess level of pain from NPWT dressing wear, since the previous study visit, using the VAS.
4. Prior to examination of the ulcer, remove compression bandaging (**for VLU subjects**) and photograph the NPWT topical dressing using the ARANZ Silhouette wound imaging and measurement device.

CONFIDENTIAL DOCUMENT

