4.3 Derived Data

1. A flag for patient inclusion in the full analysis set. If the patient has received NPWT and has at least one (post-baseline) dressing change assessment then the patient is included in the full analysis set. Otherwise the patient is excluded from the full analysis set.
2. A flag for patient inclusion in the safety population. If the patient has received NPWT, then the patient is included in the safety population. Otherwise the patient is excluded from the safety population.
3. The duration in days between the baseline assessment (Randomization Study Visit 1) and each scheduled Study Visit (2-12) (scheduled every 7 days) and Study Visit 13 or 14.

ST:

9 7 5

Reference:

CE/052/PIC

Customer Code:

0 5

4. The duration in days between the Screening Run-In Visit 1 and Screening Run-In Visit 2.
5. A flag for whether the Screening Run-In Visit 2 occurred 7 (± 1) days after Screening Run-In Visit 1.
6. The duration in days between the baseline assessment (Randomization Study Visit 1) and each scheduled Study Visit (2-12) (scheduled every 7 days) and Study Visit 13/14.
7. A flag for whether study visits occurred weekly after the Randomization Visit as per the protocol. A separate flag should be derived for each study visit.
E.g. Study Visit 2 should occur at 7 (± 1) days after the Randomization Study Visit 1. Study Visit 3 should occur at 14 (± 1) days etc.
8. The duration in days between the Study Visits i and j (where $i \geq 1$ and $j = i + 1$)
9. Patient age (years) defined as: The date of the baseline assessment – date of birth/365.25
10. Patient body mass index defined as: $\text{Weight (kg)} / (\text{Height (cm}/100))^2$
11. Reference wound duration at point of randomisation will be derived as follows:
Date of Target onset date - Date of Randomization Visit 1
12. The (post-screening) study duration (in days) will be derived as follows:
Date of Study Completion - Date of Randomization Visit 1
13. The Screening duration (in days) will be derived as follows (separately for screening, re-screen 1 and re-screen 2 where appropriate):
Date of Run-In Visit 2 - Date of Run-In Visit 1
14. The number of screening periods per subject will be derived as:
No re-screening periods used = 1
A single re-screening period used = 2
Two re-screening periods used = 3

Document Number: 1004313
Document Version: 06

Document Part: 000
Document Status: Released

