4.6 Protocol Deviations

The occurrence of the following examples of protocol deviations and significant protocol deviations, and the number of subjects with a protocol deviation and significant protocol deviation will be summarized:

- Patients that do not meet the inclusion/exclusion criteria but are randomized (the reason for failure of inclusion/exclusion criteria will be summarized)
- Subjects with a PICO duration of dressing wear is >7 days where no wound filler is used
- Subjects with an ActiV.A.C.®, or PICO in combination with a wound filler, with a duration of dressing wear >3 days
- Missed Study Visit

- Patients that receive study treatment with NPWT for greater than 85 days (12 weeks allowing +1 day)
- Patients taking a prohibited concomitant medication
- Patients with a serious device related adverse event who are not withdrawn from study treatment
- Attendance of weekly Study Visit outside ± 1 day window
- Failure to complete the Subject Exit survey or Health Related Quality of Life questionnaires (EQ-5D or CWIS) at the required timepoints

Document Number: 1004313

Document Part: 000

Document Version: 06

Document Status: Released

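### The 6-day PICO kit limit for moderately exuding wounds is shorter than the 7-day visit interval, and the SAP wear flag, set above 7 days at any exudate level, does not catch the excess

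*Protocol*

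**What the plan says.** - **Usage limit.** Protocol 6.2 gives the kit a "maximum of 7 days on low exuding wounds and 6 days on moderately exuding wounds". It adds that duration may be shorter for several reasons, exudate among them, and that PICO may be used with or without a filler.
- **What a kit is.** Protocol 6.1: "Six (6) sizes of dressing are available in kits which contain 2 dressings, 1 pump and secondary fixation strips".
- **Who is eligible.** On exudate, Protocol 7.3 excludes only "Ulcers which are deemed as highly exuding, per the Investigator's discretion". Appendix 18.9 gives maximum wound areas for moderate exudate, so such wounds are an intended use.
- **Visit interval.** At Study Visit 1 (Protocol 9.1.3) subjects are told to "return to the office for Study Visit 2 in 7" (±1) days, and 9.1.4 repeats the interval for later visits. Protocol 9.1.4: "A plus or minus one day visit window will be used for all study visits". SAP 4.3 counts its windows from randomization: "Study Visit 3 should occur at 14 (± 1) days etc".
- **Between-visit change.** Protocol 9.1.3 and 9.1.4: "Subjects using a negative pressure filler dressing will be instructed to complete a dressing change in 2-3 days from application". Protocol 9.1.7 adds tNPWT users. No section gives such an instruction for PICO without filler.
- **Deviation rule.** SAP 4.6 lists, among its examples: "Subjects with a PICO duration of dressing wear is >7 days where no wound filler is used". Exudate level plays no part in it. PICO with a filler has a separate threshold of more than 3 days.

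**The concern.** For one group of eligible subjects the scheduled interval between re-applications is longer than the protocol's own limit on the device, and the SAP rule that should detect over-long wear is set at a value that lets this pass. If the sections are followed as written and nobody orders an extra change, PICO is used past its stated limit in the test arm without any record of a deviation.

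Two things are at stake. One is use of the test device within its stated limit. The other is whether the deviation record for the PICO arm means what it appears to mean. The primary non-inferiority analysis is run in the Per Protocol Population, which excludes significant protocol deviations, so a wear rule that disagrees with the protocol could affect who is in that analysis.

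**Working it through.** **Inputs.** Kit limit: 7 days (low exudate) or 6 days (moderate exudate), Protocol 6.2. Interval from the previous visit: 7 ± 1 = 6 to 8 days, Protocol 9.1.3 and 9.1.4. SAP flag for PICO without filler: wear above 7 days, SAP 4.6. SAP wear per dressing = removal date − application date − interruption of study therapy, SAP 4.3 item 26.

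**Interval under the SAP windows.** With windows counted from randomization, two consecutive in-window visits are 7 + b − a days apart, where a and b are each −1, 0 or +1. The range is 7 − 1 − 1 = 5 to 7 + 1 + 1 = 9 days.

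**Excess over the limit.** PICO without filler, one dressing worn from visit to visit, no interruption:

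| Days between visits | Over the 7-day limit (low) | Over the 6-day limit (moderate) | SAP flag (>7) |
|---|---|---|---|
| 5 | none | none | no |
| 6 | none | none | no |
| 7 | 7 − 7 = 0 | 7 − 6 = 1 | no |
| 8 | 8 − 7 = 1 | 8 − 6 = 2 | yes |
| 9 | 9 − 7 = 2 | 9 − 6 = 3 | yes |

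The only row where the limit is exceeded and nothing is flagged is day 7 with moderate exudate, and day 7 is the nominal visit day. Table 17-1 schedules applications at Study Visits 1 to 12, so the upper bound is 12 such applications per subject. Reaching it requires moderate exudate, no filler and no interim change in every week.

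**Two further unflagged routes without filler.**

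1. Interruption: an 8-day interval with a 1-day interruption counts as 8 − 1 = 7 days of wear, which is not above 7.
2. Unit: the limit is per kit and the flag is per dressing. If both dressings of one kit are worn 4 + 4 days, the kit reaches 8 days, past either limit, while no dressing exceeds 7. The unit is not clear within Protocol 6.2 itself, which describes the system as a pump plus two dressing kits, whereas 6.1 uses the word kit for the whole set.

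**With filler.** The more-than-3-days rule applies, so this gap does not arise.

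**The case against.** The strongest reply is that the weekly visit is an assessment schedule and does not fix the wear time. SAP 2.1 allows dressing changes whenever the investigator or the instructions for use require them, Protocol 6.2 expects more frequent changes in some wounds, and unscheduled changes are recorded and enter the wear calculation. This stands: a site can keep every subject within the limit. But filler and tNPWT users are given an explicit change time, while moderately exuding subjects without filler are given none, and the SAP flag would not show that a change had been missed. The SAP list is also only a set of examples; even so, this example carries a numeric threshold that does not reflect the 6-day limit.

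Four stronger readings are tempting, and the documents do not support them.

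- *On-schedule subjects in general exceed the limit unflagged.* A low-exuding subject seen on day 7 is exactly at the limit, and a single dressing worn 8 days without interruption is flagged at either exudate level.
- *The SAP threshold disagrees with the protocol in both directions.* For low exudate, above 7 days agrees with the 7-day maximum. A day-8 visit can be in window while the wear is too long, because the visit window and the wear limit are separate rules. The threshold departs from the limit only for moderate exudate.
- *Per Protocol membership follows this threshold.* Protocol 10.1 and SAP 4.4 exclude only significant deviations, and SAP 4.6 does not say which of its examples are significant.
- *Subjects are harmed or the device fails.* The documents give no data comparing day 7 with day 6. The earlier proof-of-concept study in Protocol 4.2 reports pressure held over 7 to 10 days; that neither shows harm nor removes the limit stated in 6.2.

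**Conclusion.** The point holds in a narrow form. Protocol 6.2, the visit schedule, the between-visit instruction and SAP 4.6 do not fit together for PICO without filler on moderately exuding wounds: without an interim change, the stated limit is passed by 1 day on the nominal visit day and the SAP does not flag it. At an in-window day 8 the limit is passed at either exudate level, and the flag works unless an interruption is netted off or the wear is split over two dressings of one kit.

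The day counts assume that one dressing, and so one kit, stays on from visit to visit. The number of subjects affected cannot be computed, because the documents give no expected share of moderately exuding or no-filler subjects. No effect on the primary result is shown; one through the Per Protocol Population is possible. The inconsistency should be corrected because it concerns use of the test device within its stated limit and is cheap to resolve.

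**What to change.** The sponsor should reconcile four places: the usage limit in Protocol 6.2, the visit interval and window in 9.1.3 and 9.1.4, the between-visit change instruction (9.1.3, 9.1.4, 9.1.7), and the wear rule in SAP 4.6. Which limit or schedule is right is for the sponsor to determine. The reconciled text should then:

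1. state whether the limit applies to the kit or to each dressing, and whether interrupted time counts towards it;
2. make the SAP flag follow the reconciled limit by exudate level, using the last recorded exudate amount on the modified Bates-Jensen tool, with a stated mapping of its categories (none, scant, small, moderate, large) to low and moderate;
3. say whether exceeding the limit is a significant deviation for the Per Protocol Population.

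The cost is wording in both documents and a small amount of derivation work. Exudate amount is already collected at study visits while the ulcer is open. It may not be recorded at unscheduled changes, so the last scheduled value would have to stand in for those dressings. If the sponsor chose to alter the visit interval or the between-visit instruction, there would also be an operational cost at the sites.
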